1.1 Study Conduct

This study will be conducted in compliance with the protocol approved by the Institutional Review Board, and according to Good Clinical Practice standards. No deviation from the protocol will be implemented without the prior review and approval of the IRB except where it may be necessary to eliminate an immediate hazard to a research subject. In such case, the deviation will be reported to the IRB according to its policies and procedures.

1.2 Background

Osteoarthritis (OA) is a common and major cause of pain and disability. An estimated 26.9 million adults in the US suffer from OA¹ and nearly 50% of adults may develop symptomatic knee OA by age 85². Knee OA affects obese individuals at a higher rate with $\frac{2}{3}$ of individuals developing symptomatic disease. The treatment for knee osteoarthritis is broad and includes: exercise and patient education; pharmacologic therapies, including oral, topical, and intra-articular medications; and surgical interventions, including total joint arthroplasty. Minor symptoms can be managed with non-opioid pain medications such as acetaminophen or nonsteroidal anti-inflammatory drugs (NSAIDs), which are the mainstay of pain management for OA. Severe and end-stage osteoarthritis can be treated with total joint arthroplasty. Unfortunately, NSAIDs can be a cause of renal failure, exacerbation of asthma and most notably, gastrointestinal hemorrhage. Number of deaths from NSAID-related gastrointestinal bleeding has been estimated at 16500³. With the significant morbidity associated with treatment of OA, there is a need to develop a new, effective, minimally invasive and safe treatment for pain related to osteoarthritis of the knee.

The principal symptom of OA pain is mediated by a number of factors. However, angiogenesis resulting in neovascularity, neural sensitization and inflammation has been described as a potential pathophysiological pathway of the deep joint pain described by many OA patients^{4, 5}. This increased vascularity in the setting of pain and OA has been the focus of recent endovascular investigation, with the proposed mechanism of embolization as a novel treatment.

Particulate embolization of geniculate artery branches supplying hypervascular joint tissue, the same technique we are proposing to treat pain from OA, has been previously described as a safe treatment for hemorrhage after total knee arthroplasty in multiple reports ^{6, 7,8,9}. In 2008, three cases were reported using 150-355 micrometer particles without any complications⁶. In 2013, a Japanese group reported the use of 1000-2000 micrometer particles in the treatment of five patients, again without complication⁹. In 2015, an author group that includes one of the Co- PIs reported outcomes from 13 cases in which there were no major complications and two minor complications (transient cutaneous ischemia)⁸. Finally, in 2016 a fourth report of 14 embolizations was published in

which there were no major complications and, again, two minor complications (transient cutaneous ischemia)⁷.

Embolization of hypervascular joint tissue for the treatment of pain has been pioneered by [name] and his colleagues, in Japan. They initially reported a case series in which they were able to reduce pain related to refractory tendinopathy and enthesopathy in multiple joints in 7 patients using an antibiotic particulate for embolization without major complication¹⁰. Subsequently, the same team published its experience with transcatheter embolization of hypervascular tissue within the shoulder joint in 7 patients diagnosed with adhesive capsulitis. The procedure successfully resulted in pain reduction without any complications¹¹. Finally, Okuno et al also published their results after synovial embolization in patients with painful OA. The procedure was performed on 14 patients and there were no major complications. There was significant pain reduction and decreased difficulty of movement at 4 months. Medication frequency also decreased after embolization¹². Most recently, the same group published a larger cohort¹³ of 72 patients with follow-up with midterm follow-up. Geniculate artery embolization was technically successful in in all patients. It was clinically successful in 86.3% of patients at 6 months and 79.8% at 3 years. MRI follow-up in patients demonstrated no osteonecrosis or other evidence of progression of degenerative changes.

The current investigation team has led efforts pioneering embolization procedures in novel targets that have proved successful^{14,15,16,17,18,19}. We have also had experience in embolization of the knee, in particular with post-arthroplasty hemorrhage⁸. The principal investigator/sponsor is also an Investigator on a pilot study of GAE for knee pain, with a current Investigational Device Exemption (IDE) at UNC Chapel Hill. With our proven experience in embolization, and in particular the local-regional anatomy, we have set forth to pursue a US study evaluating embolization as a treatment for OA related knee pain versus placebo to demonstrate the actual effect of embolization on pain and disability.

1.3 Medical Device

1.3.1 Name of Investigational Device

Gel-Bead embolization spheres; OptiSphere embolization spheres

1.3.2 Intended Use of the Investigational Device

Gel-Bead embolization spheres; OptiSphere embolization spheres will be used for geniculate artery embolization (GAE) in subjects with knee osteoarthritis.

1.3.3 Description of the Investigational Device

Gel-Bead embolization spheres; OptiSphere embolization spheres were found to be substantially equivalent and cleared medical devices (Premarket Notification K133237) to prior technologies:

• Emboshpere Microshperes (Biosphere Medical, Inc/Merit Medical Systems, Inc, K021397), and

Identified in the Code of Federal Regulations 21 Part 870- Subpart D-Cardiovascular Prosthetic Devices.

Classification Name: Artificial Embolization Device. Class II Medical Device Common Name: Vascular Embolization Device Subpart D-Prosthetic Devices; Sec. 870.3300

Indication for Use: Gel-Bead embolization spheres; OptiSphere embolization spheres is intended for use in embolization of hypervascular tumors.

The Gel-Bead embolization spheres; OptiSphere embolization spheres (Gel-Bead) consists of biodegradable gelatin spheres pre-filled in a 20ml syringe. The syringe contains 1 ml of spheres suspended in 5 ml of saline. Gel-Bead is offered in four size ranges: 100-300 um, 300-500 um, 500-700 um and 700-1000 um. The spheres are intended to be used with a delivery catheter with an inner diameter that is adequate for sphere delivery (not included). The finished product is sterilized by Gamma irradiation and is intended for single use only. They come in a liquid suspension that is mixed with iodinated contrast before use. Once a catheter has been fluoroscopically guided into the target vessel, the embolization spheres are then injected, causing obstruction at the arteriole level until the desired degree of embolization has occurred. The embolization spheres used during the study will be unchanged.

1.4 Preclinical Data

Gel-Bead embolization spheres; OptiSphere embolization spheres have proven to be an effective embolization material with high biocompatibility in non-human studies. A GLP animal study was conducted on twelve mature miniature swine, with animals survived up to 12 weeks following implantation²⁰. Eight animals were implanted with Gel-Bead and four animals implanted with a control (Embosphere). Gel-Bead spheres were consistently and reliably implanted in the selected target arteries of appropriate size and not in additional non-target tissues or regions. All instances of Gel-Bead delivery resulted in successful arterial occlusion at the time of implant, as confirmed by angiography. There were similar well-demarcated foci of infarction, indicative of successful embolization, observed in the target organs of both test article and control article animals. There were no clinically significant abnormalities identified in the clinical pathology blood results that negatively reflected on either the test or control devices. Examination of the tissues distant to the implantation sites did not identify any systemic abnormalities. Verification, animal study, and biocompatibility test results met the specified acceptance criteria and did not raise new safety or performance issues. Therefore, Gel-Bead is substantially equivalent to the predicate devices.

1.5 Clinical Data to Date

Gel-Bead embolization spheres; OptiSphere embolization spheres is substantially equivalent to predicate microsphere devices such as Embosphere. Embosphere

has have been safely used as an embolic agent to target hypervascular lesions throughout the body including uterine fibroids ²¹, benign prostatic hyperplasia²², meningioma²³, and adenomyosis²⁴. The investigators have also performed GAE for knee hemarthrosis with technical and clinical success using Embosphere microspheres⁸. Recently, embolization spheres have been used safely and effectively for GAE to treat knee pain in the setting of osteoarthritis¹². Gel-Bead embolization spheres; OptiSphere embolization spheres are FDA approved for the treatment of arteriovenous malformations and hypervascular tumors.

2.0 Study Objectives

The primary aim of this study is to determine if GAE will reduce the severity of pain as well as global disability (resulting from the combination of pain, stiffness and difficulty performing daily activities) caused by knee OA compared with placebo. The secondary aim is to determine if GAE can result in the decreased necessity for ongoing conservative OA therapies such as medication therapy and joint injections.

3 Study Design

3.1 General Design

This will be a single-blinded randomized-controlled study of GAE versus placebo in a small population with knee pain secondary to arthritis to determine safety and efficacy. After IRB approval of a written informed consent and over, approximately a 24 month duration, N=21 subjects will be recruited. Only subjects ≥ 40 years will be screened for study recruitment. Subjects will be randomized in a 2:1 ratio of GAE:Placebo and will be blinded from study treatment (see flow chart below). The placebo procedure will be a diagnostic angiogram of the knee, without embolization. Appropriate measures will be taken to ensure patients and nursing staff caring for the patient are blinded to assignment. Each patient will be told at the time of recruitment that they may be randomly assigned to sham, but if after 1 month they have not had symptom improvement, their assigned procedure would be revealed and, if they had undergone a sham procedure, they will be allowed to proceed with embolization. This second procedure should be shorter than a complete angiogram and embolization, as the detailed angiogram will not need to be repeated, and therefore both arms will have similar total radiation dose.

Clinical procedures and evaluations will consist of a preoperative screening assessment to determine if the potential study subject meets the inclusion and exclusion criteria, enrollment, surgical procedure for geniculate artery embolization, and follow-up visits at 24 hours, 2 weeks, 1, 3, 6, & 12 months. An MRI will be performed after the 1-month visit in those patients who underwent embolization to detect a change in synovial vascularity and to exclude complication.

3.2 Primary Study Endpoints

1. Overall efficacy of treatment as determined by a minimal clinically significant reduction in global Western Ontario and McMaster University

Osteoarthritis Index (WOMAC) questionnaire scoring of 16% at 1 and 6 month follow-up.

2. Minimal clinically important decrease of 15% on the pain VAS at 1 or 6 months follow-up.

3.3 Secondary Study Endpoints

1. Reduction of previously initiated OA medical therapy (e.g. NSAIDs) at 12 months follow-up.

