4.1 General Characteristics of the Proposed Subject Population

Study subjects will be men and women with knee osteoarthritis resulting in knee pain that is refractory to conservative therapies, who are not planning to undergo surgery within 12 months.

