5.3 Subject Compliance Monitoring

Study coordinators and physicians will inquire of the subjects to determine if they have escalated any current or initiated any new conservative therapies during the follow-up period.

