5.4 Prior and Concomitant Therapy

The subjects will be required to have been on conservative therapy for OA for at least three months prior to undergoing GAE. They will be allowed to continue previously initiated therapies throughout the study period, but if new or escalated therapies are required past the post-operative period (14 days), the treatment will be considered a failure.

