6.14 Visit 8a, 8b, or 12c-12 month follow-up for all subjects

Subjects will be seen in clinic or contacted by phone or by teleconference per, the subject's preference, 180 +/- 10 days following GAE. The WOMAC questionnaire and VAS pain score will be completed and subjects will be evaluated for possible adverse events. Subjects will also provide an update about the necessity/frequency of pre-established conservative therapies. If an AE is suspected based on change in pain scores or functionality, an appropriate work-up will be performed which may include MRI.

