We will identify extreme primary endpoint values by computing studentized residuals and then conduct sensitivity analyses by deleting these outliers from the analysis datasets. We will repeat the above statistical tests and use results of the sensitivity analyses to corroborate conclusions reached in the primary analyses.

We will address the secondary study endpoint of reduction of OA by comparing frequency of OA medical therapy between the sham group, the crossover group, and the GAE group at 12 months. We will employ a chi-squared test to test the H_0 : frequency of OA medical therapy is equal for between the sham group, the crossover group, and the GAE group versus the one-sided alternative hypothesis. A p-value of < 0.05 will be taken as evidence to suggest that the frequency of OA medical between the groups. Non-significance of the p-value for this test will be considered inconclusive evidence against the null hypothesis.

Reduction in AE will be evaluated with a multilevel logistic regression model. The outcome of adverse events will be regressed on treatment status. We will employ a compound symmetric R-side covariance structure to account for dependencies arising from observations from the same patient. The H_0 : frequency of AE is equal for between the sham group and the GAE group will be assessed versus the two-sided alternative hypothesis with a statistical test of the treatment

parameter different than 0, with a p-value of < 0.05 taken as evidence to suggest that the frequency of OA medical therapy is not equal between the groups. Non-significance of the p-value for this test will be considered inconclusive evidence against the null hypothesis.

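### Sections 3.3, 5.3, 5.4, 6.5–6.14 and 8.2 define OA therapy differently, so the only secondary endpoint has no settled score for a subject who replaces one therapy with another

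*Combined protocol and SAP*

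**What the plan says.** Section 3.3 lists a single secondary endpoint: "Reduction of previously initiated OA medical therapy (e.g. NSAIDs) at 12 months follow-up". The aim behind it, in section 2.0, is "decreased necessity for ongoing conservative OA therapies such as medication therapy and joint injections". For the 12-month visit, section 6.14 states: "Subjects will also provide an update about the necessity/frequency of pre-established conservative therapies". The same sentence appears for the 1, 3 and 6 month visits (6.5, 6.6 and 6.8, and 6.11 to 6.13 for Arm C).

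Three other sections use a wider scope:

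- Section 5.3, on compliance, has coordinators and physicians question subjects to "determine if they have escalated any current or initiated any new conservative therapies during the follow-up period".
- Section 5.4 rules that "if new or escalated therapies are required past the post-operative period (14 days), the treatment will be considered a failure".
- Section 8.2 addresses the secondary endpoint by "comparing frequency of OA medical therapy between the sham group, the crossover group, and the GAE group at 12 months", and continues: "We will employ a chi-squared test to test the H_0 : frequency of OA medical therapy is equal". Neither sentence limits the therapy to what was in use before the procedure.

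Section 7.2 defines clinical success from WOMAC and VAS alone. Surgery appears in section 4.1, where the population is described as people "who are not planning to undergo surgery within 12 months", but in no endpoint rule.

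**The concern.** Subjects enter with pain that conservative care has not controlled, and they are followed for 12 months. Some can be expected to stop one therapy because they start another. Such a subject has not reduced the need for therapy. An endpoint that looks only at the earlier therapy would nevertheless record a reduction.

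Two things are at stake. First, a replacement could be scored as a benefit, with small denominators that make each case count. Second, because the sections differ, the scoring rule could be chosen after the data are seen, when the choice affects the result.

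**Working it through.** **The plan's own figures.** The power figures in section 8.1 concern WOMAC and VAS. No sample-size or rate figure is given for the secondary endpoint, so there is nothing to reproduce here. The check is a comparison of the sections, followed by the weight of one subject.

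**Step 1: apply each section to the same records.** The four records are hypothetical. Each subject takes a daily NSAID at baseline.

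| Record | 3.3 with the visit question | 8.2 (use at month 12) | 5.4 |
|---|---|---|---|
| A. No NSAID at month 12, nothing new | Reduction | No use | Not a failure |
| B. NSAID stopped at month 4; a new drug is required and still taken at month 12 | Reduction | Use | Failure |
| C. NSAID stopped at month 4; a new joint injection is required | Reduction | Not settled: 8.2 does not say whether an earlier injection counts as month-12 use | Failure |
| D. Knee surgery at month 8; no NSAID at month 12 | Reduction | No use | Not settled: 5.3 asks only about conservative therapy, though 5.4 could be read to include surgery |

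Only record A gets one consistent answer. Record B gets contradictory answers from 3.3 and 8.2, although 8.2 presents its test as the analysis of the 3.3 endpoint. If 8.2 takes over the 3.3 definition, B is a reduction. If it does not, the endpoint and its test measure different things. Records B and C can be a 5.4 failure and a 3.3 reduction at once, because neither 3.3, 7.2 nor 8.2 uses the failure status.

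**Step 2: weight of one subject.** Inputs are N = 21 and 2:1 allocation (section 3.1).

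- GAE: 21 × 2/3 = 14; one subject = 1/14 = 7.1 points.
- Initial sham: 21 × 1/3 = 7; one subject = 1/7 = 14.3 points.
- Section 8.2 separates sham-only from crossover. If m subjects remain in one of those groups, one subject is worth 1/m, which exceeds 14.3 points whenever m is below 7.

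**Step 3: direction.** A replacement scored as a reduction in the GAE group favours GAE. One in the sham group works against GAE.

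An illustration with assumed counts: let true reduction be 6/14 in GAE and 3/7 in sham, 43% in each. Let k GAE subjects who replaced a therapy be scored as reductions. Two-group chi-squared without correction gives:

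| k | GAE scored as reduced | p |
|---|---|---|
| 0 | 6/14 = 43% | 1.00 |
| 2 | 8/14 = 57% | 0.54 |
| 4 | 10/14 = 71% | 0.20 |
| 6 | 12/14 = 86% | 0.04 (Fisher exact 0.12) |

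In the other direction, one such subject in sham moves it from 3/7 = 43% to 4/7 = 57%. The planned test has three groups, so these p-values show sensitivity only and predict nothing.

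**The case against.** The best reply is that the protocol already deals with replacement. Section 5.4 classes required new or escalated therapy after day 14 as failure, and 5.3 collects the information. Inclusion criterion 2 (section 4.3) lists intra-articular injections among conservative therapies, so 5.3 covers new injections. The tested variable in 8.2 is not restricted to earlier therapy, so a new drug at month 12 counts as use. The aim in 2.0 speaks of ongoing therapies, which is close to the 3.3 wording. Surgery should be uncommon in people not planning it.

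Much of this stands, and it rules out two stronger readings.

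- **A reader might infer that new therapy goes unrecorded.** It does not: 5.3 has staff ask about it.
- **A reader might infer that subjects who switch will be scored as successes and that the contrast will therefore shrink.** For example, suppose true use is 6/7 in sham and 7/14 in GAE, a contrast of 85.7% − 50.0% = 35.7 points. If two sham users switch and are no longer counted, the contrast becomes 4/7 − 7/14 = 57.1% − 50.0% = 7.1 points. The documents do not support this as a prediction. The counts are invented. All seven sham subjects would have to remain uncrossed, although those without improvement at 1 month are offered GAE. Under the 8.2 wording the two switchers still count as users, so the contrast stays at 35.7 points.

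The reply does not supply a scoring rule. Section 5.3 is not linked to 3.3 or 8.2, the 5.4 status is used in no analysis, and the wider wording of 8.2 conflicts with 3.3 without replacing it.

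**Conclusion.** The point holds as an unreconciled definition. On the literal wording of 3.3 and the visit sections, a subject who replaces an earlier therapy with a new drug or injection counts as a reduction. Under 8.2 a new drug counts as use. Under 5.4 the same subject is a failure if the new therapy was required after day 14, but that status has no effect on any result. Knee surgery has no rule at all.

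The size per affected subject is 7.1 points in GAE and 14.3 points in the initial sham group, assuming full 14:7 enrollment. The total effect and its direction cannot be stated, because the documents give no rate of switching or surgery. The primary endpoints are not affected. This should be settled before data are analysed, since it concerns the only secondary endpoint and the groups are small.

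**What to change.** Define one variable, in the same words, in 3.3 and 8.2: all OA therapy in use at month 12, both pre-existing and new and including injections, compared with baseline. A replacement is then not scored as a reduction.

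Change the therapy question in 6.5, 6.6, 6.8 and 6.11 to 6.14 so that it covers all OA therapies, old and new. Confirm that the baseline case report form records therapy in the same form, since 6.1 mentions a history without naming therapy.

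Reconcile 3.3 and 8.2 with 5.4 by stating how 5.4 failures and subjects with knee surgery are counted in this endpoint. It is not necessary to score everyone who ever started a new therapy as not reduced. That would turn a month-12 status into an any-time composite, which is a separate and debatable choice.

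The cost is wording in these sections and one case report form line, because 5.3 already has staff seek the information. The downside is that fewer subjects will be scored as having reduced therapy.

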3.4 Primary Safety Endpoints

1. GAE without major complication.

4 Subject Selection and Withdrawal

4.1 General Characteristics of the Proposed Subject Population

Study subjects will be men and women with knee osteoarthritis resulting in knee pain that is refractory to conservative therapies, who are not planning to undergo surgery within 12 months.

